13.3.4 Ventilator-free days

Summary statistics (mean, median, standard deviation [SD], minimum, and maximum) of VFDs over 28 days will be presented by treatment group. Missing data will be handled using a last observation carried forward (LOCF) approach when calculating VFDs for each patient. A histogram of VFD will also be produced for each treatment group.

For the formal statistical analysis, an analysis of covariance model will be fitted for VFDs allowing for treatment group and the following baseline covariates:

APACHE II score (four categories based on the quartiles of the baseline score), age (two categories: <60 and 60 or older), region (three categories: Australia, North America [Canada & USA] and All Other) and an indicator variable if the patient was on mechanical ventilation at baseline (two categories: yes or no).

The difference in VFDs for each of the comparisons: AZD9773 dose 1 versus placebo, AZD9773 dose 2 versus placebo, AZD9773 dose 1 and 2 versus placebo will be presented in terms of the difference in the Least Square Means (LSMeans) and the associated two-sided 80% CI and one-sided p-value. Additionally, a two-sided 95% CI and two-sided p-value will also be presented.

For the PP population, the effect of other baseline variables (examples include baseline TNF, Xigris use prior to study treatment and presence of shock at baseline) on the treatment comparisons will also be explored via a series of analyses including the covariates as specified above for each of the levels of these baseline variables separately. The difference in the treatment LSMean and the associated two-sided 80% CI from these analyses (along with the results from the baseline covariates fitted in the statistical analysis above) will be presented graphically on the same plot. Additionally, an analysis of variance will also be performed for the PP and ITT populations (with no covariates and only treatment as a factor).

VFDs at Day 15 (over 14 days) will be analysed in a similar manner to above.

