13.3.6 Organ failure-free days, shock-free days, and ICU-free days

Organ failure-free days, shock-free days, and ICU-free days will be summarised and analysed in the same way as for VFD (see Section 13.3.4).

13.3.7 7-day mortality, 28-day mortality and mortality at Day 90

Seven-day mortality and 28-day mortality will be summarised by treatment group. The formal analysis will be undertaken for each the comparisons: AZD9773 dose 1 versus placebo, AZD9773 dose 2 versus placebo, AZD9773 dose 1 and 2 versus placebo separately using a Cochran-Mantel-Haenszel test in which the test will be stratified using the same covariates as for VFD. The corresponding relative risk, two-sided 80% CI and one-sided p-value will be calculated using the procedure PROC FREQ in SAS. Additionally, a two-sided 95% CI and two-sided p-value will also be presented.

An unstratified analysis will also be performed for the PP and ITT populations. Additionally, for the PP population, the impact of other baseline variables (examples include baseline TNF, Xigris use prior to study treatment and presence of shock at baseline) on the treatment comparisons will be explored by undertaking a series of analyses for each of the levels of these baseline variables separately, and the relative risks along with the associated two-sided 80% CIs from these analyses will be presented graphically.

In the event that the 7-day mortality and 28-day mortality status is unknown for some patients, they will be excluded from the PP population. However, for the ITT population they will be included as though they had died. Further sensitivity analyses may be undertaken depending on the number of such patients.

A Kaplan-Meier curve of time to death will also be produced and both a stratified (using the same covariates as for the analysis of 7 and 28-day mortality) and unstratified log rank test will be undertaken. If the 7-day or 28-day mortality status is unknown for some patients, they will be censored at the last known date the patient was alive.

Mortality at Day 90 will be considered in the same way as 7-day and 28-day mortality.

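### The formal mortality tests are stratified into 48 crossed cells, which costs about 20–23% of the CMH information in each dose–placebo comparison; a coarser stratification recovers most of it

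*Protocol*

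**What the plan says.** Section 13.3.7 makes the formal mortality analysis a test for each of the three comparisons (each dose versus placebo, and both doses combined versus placebo) "using a Cochran-Mantel-Haenszel test in which the test will be stratified using the same covariates as for VFD". For time to death it plans "both a stratified (using the same covariates as for the analysis of 7 and 28-day mortality) and unstratified log rank test will be undertaken". The synopsis describes the same stratification.

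The covariates are defined in section 13.3.4. Severity of illness has four levels: "APACHE II score (four categories based on the quartiles of the baseline score". The remaining three are age, split into two groups at 60 years; geographical region, in three groups; and whether the patient was being ventilated at baseline, in two.

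Nothing in the protocol pools, limits or collapses the resulting cells. Section 6.2.1 states that randomisation is not stratified. Section 13.3.7 also plans an unstratified mortality analysis in the PP and ITT populations. Section 13.1 says that the study is not powered for mortality and that confidence intervals will guide interpretation.

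**The concern.** The same covariate list does different work in the two analyses. In the ANCOVA for ventilator-free days the four covariates enter as main effects and cost 3 + 1 + 2 + 1 = 7 parameters. In a CMH or stratified log-rank test they are crossed, and every cell becomes its own comparison. A cell that holds only one arm, or has no deaths or only deaths, contributes nothing to the CMH test. Because allocation is not balanced within cells, many cells will be of this kind.

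At stake is precision in the formal adjusted mortality analysis. The plan relies on the mortality intervals because the tests lack power. Section 4.2 says that the trial is to choose the regimen for later studies of 28-day mortality, and the single-dose comparisons that inform this choice lose the most.

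**Working it through.** **Inputs from the protocol.** About 300 patients, 100 per arm, 1:1:1 (synopsis; section 4.1); one-sided 10% level (section 13.1); covariate levels (section 13.3.4); 28-day mortality of 37% on placebo and 26% on active in the earlier D-CytoFab study (section 2.1.4), used for illustration.

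**The plan's own power figure.** It concerns ventilator-free days: difference 4.2, SD 11.380, 100 per group. 4.2 / (11.380 × √(2/100)) = 4.2 / 1.609 = 2.610; 2.610 − 1.282 = 1.328, which gives power 0.908. The stated 90% reproduces. The protocol gives no power for mortality and no number of strata.

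**Number of strata.** 4 × 2 × 3 × 2 = 48. Patients per cell: 200/48 = 4.2 for one dose versus placebo; 300/48 = 6.3 for combined doses versus placebo.

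**Expected information loss.** Stratum h contributes information proportional to n1h·n0h/nh. When allocation ignores the strata, the expected sum over K non-empty strata, relative to the unstratified value, is (N − K)/(N − 1), so the loss is (K − 1)/(N − 1). K depends on how the cells fill, which the protocol does not give. Three assumed patterns were tried, with 3,000 simulated trials per setting:

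| Assumed fill | K | Formula | Simulated loss |
|---|---|---|---|
| Uniform, N = 200 | 47.3 | 46.3/199 = 23.3% | 23.2–23.4% |
| Region 20/50/30, 65% ventilated, N = 200 | 45.3 | 44.3/199 = 22.3% | 22.1–22.3% |
| Region 15/55/30, 80% ventilated, correlated covariates, N = 200 | 40.0 | 39.0/199 = 19.6% | 19.5–19.6% |
| Second pattern, combined doses, N = 300 | 47.0 | 46.0/299 = 15.4% | 15.3–15.4% |

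With 8 strata, all filled, the same formula gives 7/199 = 3.5% and 7/299 = 2.3%. The stratified log-rank with 48 strata lost 20–27% in the two uneven single-dose patterns.

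**Patients in cells that contribute nothing (28-day mortality, single dose).** 20–32% when the covariates are not prognostic to moderately prognostic, and 38–46% when they are very strongly prognostic. For 7-day mortality at an assumed 15% versus 9%, 54%.

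**CMH power, 37% versus 26%, 100 per arm, one-sided 10%** (ranges over the three patterns; prognostic strength is assumed):

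| AUC of covariates | 48 strata | Unstratified | 8 strata |
|---|---|---|---|
| 0.50 | 58% | 64–66% | 64–65% |
| about 0.60 | 58–59% | 65–66% | 64–65% |
| about 0.67–0.68 | 59–62% | 65% | 66–67% |
| about 0.75–0.76 | 63–65% | 64–66% | 69–70% |
| about 0.82–0.84 | 68–72% | 65–67% | 74–76% |

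In these runs 48 strata trailed 8 by about 4–7 points in the single-dose comparisons. For combined doses they gave 70–73% against 75–78%; another set of runs put that gap at 2–4 points. With 80 per arm, to illustrate a smaller PP set, power was 50% against 58%. Hence about 2–8 points overall.

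**Precision.** The standard error of the log relative risk was 4–12% smaller with 8 strata than with 48 in one set of runs, and 8–13% larger with 48 than with 8 in another.

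**Main-effects model.** In one further setting (4,000 trials; region 15/45/40, 70% ventilated, moderate effects, odds ratio 0.61) power was 52% with 48 strata, 56% unstratified, 58% with 8 strata and 59% for a logistic model with main effects. Rejection under the null was 0.096–0.099 for all four.

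**The case against.** A reader might infer that 48 strata do worse than no stratification, that the 22% is a net loss, or that the relative-risk interval must be wider than the unstratified one. The documents do not support any of these. The information figure counts only the thinning of cells and leaves out the outcome variance that stratification removes. That gain depends on prognostic strength, for which the protocol gives no figure. In the table, 48 strata lose 6–8 points to the unstratified test when the covariates carry little or no prognosis, are about level at an AUC near 0.75, and gain 1–6 points near 0.83. The interval behaves alike: the standard error of the log relative risk, 48 strata against unstratified, was 0.245 v 0.216 with no prognosis, 0.227 v 0.217 at an AUC of 0.71 and 0.212 v 0.217 at 0.785.

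It is also fair to say that the sparse CMH test remains valid, that unstratified analyses are already planned, that mortality is secondary and declared not powered, and that the combined comparison loses only about 15%. A pooling rule could appear in the SAP, which is not to hand.

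All of this lowers the stakes. It does not remove the point, because the protocol itself fixes stratification on all four covariates, and the formal adjusted analysis is weaker than a coarser one that is not planned. An endpoint short of power is a reason to preserve information.

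**Conclusion.** The stratification is too fine for the sample. The 48 cells, about 4 patients per cell and the unstratified randomisation come straight from the protocol. The CMH information loss of 20–23% per single-dose comparison (about 15% combined) follows from them with little dependence on assumptions. The 20–27% for the log-rank comes from simulation under two assumed patterns.

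The comparison with 8 strata rests on assumed covariate mixes and prognostic strengths, and on 37% versus 26% mortality. Within that range the direction never changed: 48 strata gave about 2–8 points less CMH power and a wider relative-risk interval. The 8-strata power figures are for the CMH test; for the log-rank, the reason to coarsen is the same thinning of cells. No bias or inflated type I error is claimed, nor that 48 strata are worse than none. This is a cheap improvement on secondary endpoints, not a threat to the primary analysis.

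**What to change.** Reword section 13.3.7 and the synopsis in one of two ways:

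- Stratify the CMH and log-rank tests by baseline ventilation and APACHE II quartile only (8 strata). APACHE II quartile alone (4 strata) performed about as well in the CMH simulations.
- Use a logistic model for mortality and a Cox model for time to death, with the four covariates as main effects, and report a standardised relative risk with 80% and 95% confidence intervals.

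Keep the unstratified analyses in either case. No new data, visits or patients are needed. The first option leaves age and region out of the stratification and can trail the unstratified test by one to two points if the covariates carry no prognosis (64.5% against 66.0% in one pattern). The second requires a model in place of a simple stratified test.

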13.3.8 PRO variables

The physical component summary score, mental health component summary score, Physical functioning and Bodily pain scales and individual question 2 of the raw data and change from baseline will be summarised (mean, median, SD, minimum, and maximum) by treatment group. Patients who complete an initial assessment at Day 29 and then subsequently die will be assigned a worst-case score for the Day 90 visit. Furthermore, as the initial value is collected at Day 29, there is the potential that the treatment groups may not be comparable in this summary. Consequently, a further summary will include ITT patients where any patients who die prior to the Day 29 assessment will be given a worst-case score at both assessments.

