7.4.5 Patient reported outcomes (PRO)

7.4.5.1 Short Form 36 Health Survey, version 2 Acute

Assessment of patients' HRQoL will be derived from the Short Form 36 Health Survey, version 2 Acute (SF-36v2 Acute) questionnaire. The SF-36v2 Acute is a multi-purpose, short-form health survey with only 36 questions, which is provided in [Appendix K](#). It yields an 8-scale profile of HRQoL scores (Physical functioning Role-physical, Bodily pain, General health, Vitality, Social functioning, Role-emotional, Mental health) as well as a psychometrically based physical (physical component score) and mental health summary (mental component score) measures and a preference based health utility index.

The SF-36v2 Acute differs from the standard SF-36 in that the recall period for 6 of the 8 scales (Role-physical, Bodily pain, Vitality, Social functioning, Role-emotional and Mental health) changes from "the past 4 weeks" to "the past week". Two scales, Physical functioning and General health do not have a recall period; the items and instructions for these scales are identical across acute and standard forms. This version was chosen for the study as the 1-week recall period seems more appropriate for these scales specifically at Day 29.

Additionally for this study, 1 further change will be made to the SF-36v2 Acute. The original question 2 from the standard version – "Compared to 1 year ago, how would you rate your health in general now?" will replace the question 2 from the acute version – "Compared to 1 week ago, how would you rate your health in general now?". This has been included to allow a better understanding of a patient's return to their pre-sepsis levels of HRQoL. As this question does not form a part of any of the main outcome measures outlined above, this does not affect the validity of these endpoints.

The SF-36v2 Acute will be completed at Day 29+2 and at Day 90+14. The Day 29 value will be the initial measurement and the Day 90 value will be taken as follow-up. The SF-36v2 Acute has been validated for multiple completion methods (face-to-face, telephone, IVRS), and the most appropriate method for the patient will be used in this study, although all assessments will be interviewer-led.

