12.2.2 Calculation and derivation of PRO variables

The SF-36v2 Acute scoring will be used (SF-36 health survey manual and interpretation guide, [Ware et al, 2000](#)). Two overall summary scores, the physical component summary score and the mental health component summary score, will be derived as the principal

method of reporting SF-36v2 Acute results. Each domain score will also be derived individually.

The Day 29 value will be taken as the initial value, and the Day 90 value will be taken as the follow-up value.

12.2.3 Calculation and derivation of Acute Physiology and Chronic Health Evaluation (APACHE) II Score

The calculation of the APACHE II score will be done electronically; investigators will only need to enter the values of the parameters measured into the eCRF.

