13. STATISTICAL METHODS AND SAMPLE SIZE DETERMINATION BY ASTRAZENECA

13.1 General principles

A comprehensive SAP will be finalised before the last patient visit. All statistical analyses will be performed by PAREXEL. Any deviations from those analyses presented here and/or in the SAP will be detailed in the clinical study report. All outputs will be produced using SAS[®] version 9 or later in accordance with AstraZeneca standards.

All study data will be analysed after the 28-day follow up is complete for all patients. A further analysis will be performed using the Day 90 assessment to understand longer-term patient outcomes (survival and HRQoL).

The following efficacy endpoints will be subject to formal statistical analysis: VFDs, 7-day mortality, 28-day mortality, mortality at Day 90, organ failure-free days, shock-free days and ICU-free days. All other data will only be summarised.

All efficacy data will be summarised and analysed using the per protocol (PP) population. Additionally, an ITT analysis of the endpoints listed above for formal analysis will also be undertaken using the ITT population.

For each of the endpoints subject to statistical analysis the following statistical comparisons will be performed: AZD9773 dose 1 versus placebo, AZD9773 dose 2 versus placebo, and combined AZD9773 dose arms 1 and 2 versus placebo. Although there are three primary comparisons, this is an exploratory Phase IIb study and consequently no adjustment for multiple comparisons will be made.

Unless stated below, no imputation of missing data will be performed. All data recorded on the database will be included in data listings. Any spurious or erroneous data will be queried and followed up until satisfactorily resolved.

The nominal significance level used for this study will be 10% one-sided. However, it is important to note that the study has only been sized based on VFDs over 28 days; this study is not powered to detect a statistically significant difference in 7-day mortality, 28-day mortality or mortality at Day 90. In this case the confidence intervals (CIs) will provide a guide to the possible range of the true treatment effect. This may also be the case for the other secondary endpoints.

Demography data will be summarised using the PP and ITT populations and safety data will be summarised using the safety population. For all summaries of change from baseline, baseline is defined as the latest non-missing assessment prior to first study drug infusion.

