Appendix K
Short Form 36 Health Survey, Version 2 Acute

THIS IS A PRINTED COPY OF AN ELECTRONIC DOCUMENT. PLEASE CHECK ITS VALIDITY BEFORE USE.

Your Health and Well-Being

This survey asks for your views about your health. This information will help keep track of how you feel and how well you are able to do your usual activities. Thank you for completing this survey!

For each of the following questions, please mark an in the one box that best describes your answer.

1. In general, would you say your health is:

Excellent	Very good	Good	Fair	Poor
▼	▼	▼	▼	▼
 1	 2	 3	 4	 5

2. Compared to one year ago, how would you rate your health in general now?

Much better now than one week ago	Somewhat better now than one week ago	About the same as one week ago	Somewhat Worse now than one week ago	Much worse now than one week ago
▼	▼	▼	▼	▼
 1	 2	 3	 4	 5

3. The following questions are about activities you might do during a typical day. Does your health now limit you in these activities? If so, how much?

Yes, limited a lot	Yes, limited a little	No, not limited at all
▼	▼	▼

- a Vigorous activities, such as running, lifting heavy objects, participating in strenuous sports..... 1 2 3
- b Moderate activities, such as moving a table, pushing a vacuum cleaner, bowling, or playing golf..... 1 2 3
- c Lifting or carrying groceries 1 2 3
- d Climbing several flights of stairs 1 2 3
- e Climbing one flight of stairs 1 2 3
- f Bending, kneeling, or stooping 1 2 3
- g Walking more than a mile..... 1 2 3
- h Walking several hundred yards..... 1 2 3
- i Walking one hundred yards 1 2 3
- j Bathing or dressing yourself 1 2 3

THIS IS A PRINTED COPY OF AN ELECTRONIC DOCUMENT. PLEASE CHECK ITS VALIDITY BEFORE USE.

THIS IS A PRINTED COPY OF AN ELECTRONIC DOCUMENT. PLEASE CHECK ITS VALIDITY BEFORE USE.

4. During the past week, how much of the time have you had any of the following problems with your work or other regular daily activities as a result of your physical health?

	All of the time	Most of the time	Some of the time	A little of the time	None of the time
	▼	▼	▼	▼	▼

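### The change output in the further ITT quality-of-life summary scores a death before Day 29 as no change; separately, SF-36 question 2 pairs a one-year stem with one-week answers

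*Protocol*

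**What the plan says.** The SF-36v2 Acute is collected only at Day 29 and Day 90 (Protocol Table 1 and section 7.4.5.1). Section 12.2.2 fixes the roles of the two visits: "The Day 29 value will be taken as the initial value, and the Day 90 value will be taken as the follow-up value". Section 13.3.8 plans mean, median, SD, minimum and maximum by treatment group, for raw values and for change, of the two component scores, Physical functioning, Bodily pain and question 2; for the last, "individual question 2 of the raw data and change from baseline will be summarised".

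Deaths are handled by two rules in section 13.3.8:

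- In the first summary, "Patients who complete an initial assessment at Day 29 and then subsequently die will be assigned a worst-case score for the Day 90 visit".
- The protocol recognises that a Day 29 starting value may leave the groups non-comparable. It therefore adds a further summary of ITT patients in which "any patients who die prior to the Day 29 assessment will be given a worst-case score at both assessments".

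On question 2, section 7.4.5.1 replaces the acute version's one-week question with the standard one-year question, so as to understand a patient's "return to their pre-sepsis levels of HRQoL". The Appendix K form carries the new stem, "Compared to one year ago, how would you rate your health in general now", but the first answer option reads "Much better now than one week ago" and the other four also refer to one week.

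**The concern.** The further ITT summary exists to repair the comparison between arms when some patients die before Day 29. Its change output does not do so. Giving the worst score at both visits makes the difference zero, so the patient with the worst possible course is recorded as stable. A patient who lives long enough to complete the Day 29 form and then dies is recorded as having deteriorated as far as that score allows. The output depends on when deaths occur, in the wrong order, and a reader of that table could take fewer late deaths or more early deaths for better quality of life.

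The question 2 issue is separate and concerns the instrument. The stem was changed so that patients would compare themselves with their health before sepsis. If the options still refer to the previous week, the recorded answer does not show which comparison was made, and no later analysis can recover it. HRQoL in survivors is a named secondary objective, and the Day 90 analysis is planned specifically for survival and HRQoL.

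**Working it through.** The protocol gives no figure to reproduce on this point, so the check is of the scoring rules themselves.

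**Which baseline applies.** Section 13.1 says that, for change summaries, "baseline is defined as the latest non-missing assessment prior to first study drug infusion". No SF-36 form is completed before the first infusion, so that definition cannot apply. With section 12.2.2, change can only mean Day 90 minus Day 29.

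**Change for each type of patient** (W = worst score, X = observed Day 29 score):

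- Death before Day 29: W - W = 0, on every scale.
- Death after a completed Day 29 form: W - X, the largest fall possible from X (zero only if X is already the worst score).
- Survivor: observed Day 90 minus X.

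An early death is therefore never scored worse than a late one.

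**Arm means.** With early-death share e, late-death share l and survivor share s = 1 - e - l:

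mean change = e × 0 + l × (W - X) + s × g, where g is the mean survivor change.

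Assumptions, none of them from the protocol: 0-100 scale, W = 0, Day 29 mean X = 40 among patients alive then, and l = 5% in both arms unless stated. For e I use 37% and 26%, the placebo and active 28-day mortality of the earlier D-CytoFab Phase IIb study (Protocol section 2.4), purely as an illustration.

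| Survivor change g | e = 37%: 0.58g - 2 | e = 26%: 0.69g - 2 | Higher mean change |
|---|---|---|---|
| -5 | -4.90 | -5.45 | more early deaths |
| 0 | -2.00 | -2.00 | tie |
| +5 | 0.90 | 1.45 | fewer early deaths |
| +10 | 3.80 | 4.90 | fewer early deaths |

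With equal late deaths the difference between arms is -0.11 × g, so its sign depends on whether survivors decline or improve.

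**Unequal late deaths**, with survivors improving by 10 and late deaths falling by 40:

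- 30% early and 0% late: 0.70 × 10 = +7.0.
- 15% early and 5% late: 0.80 × 10 - 0.05 × 40 = +6.0. Total mortality is 20% rather than 30%, yet this arm looks worse.
- With 5% late deaths in both arms, the arm with 30% early deaths has 0.65 × 10 - 2 = +4.5 against +6.0, so the order reverses.
- With no late deaths in either arm: +7.0 against 0.85 × 10 = +8.5.

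**Timing alone.** With 31% deaths and g = 0, mean change is 0.0 if all deaths are early and 0.31 × (-40) = -12.4 if all are late. The raw Day 90 mean is 0.69 × 40 = 27.6 in both cases.

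**Raw scores in the same summary.** Day 29 means are 0.63 × 40 = 25.2 (e = 37%) and 0.74 × 40 = 29.6 (e = 26%). At g = +10 the Day 90 means are 0.58 × 50 = 29.0 and 0.69 × 50 = 34.5, a gap of 5.5 points against 1.1 for change. The raw scores show the mortality difference; the change output shrinks it.

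**Question 2.** Patients enter with acute sepsis and are dosed within 24 hours of organ failure. One week before Day 29 or Day 90 therefore falls after sepsis onset, while one year before falls ahead of it. A recovering patient may truthfully be better than a week ago and worse than a year ago. The stem and the options can thus call for opposite answers.

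**The case against.** The strongest reply is that little rests on this output. PRO data are outside the list of formally analysed endpoints and are only summarised. Mortality at 7, 28 and 90 days is compared formally, with Kaplan-Meier curves, so a difference in deaths will be visible elsewhere. The raw Day 29 and Day 90 scores are already planned in the same ITT summary and correctly penalise early death. The synopsis names the SF-36 outcome as scores at the two visits, not as change. All of this stands, and it limits the weight of the point.

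A reader might infer that an arm with more early deaths will show the better mean change. The documents do not support that as a general statement: with improving survivors and equal late deaths, the arm with more early deaths has the lower mean, as the table shows. The +7.0 against +6.0 result needs late deaths in one arm only. What remains is that the rule never ranks an early death below a late one, and that the direction of the distortion depends on quantities unrelated to the purpose of the summary.

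On question 2, section 7.4.5.1 states that the item is outside the main measures, and completion is interviewer-led. The first limits the damage to one output. The second does not cure it, since interviewers may resolve the conflict differently and nothing in the planned recording shows how. A reader might also infer that every form in use is affected. Only Appendix K is shown; the fielded and translated forms are not.

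**Conclusion.** Both defects are in the protocol as written.

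In the further ITT summary, the change output assigns 0 to a death before Day 29 and the largest available fall to a death after a completed Day 29 form. It can favour the arm with more early deaths when survivors decline or when the other arm has more late deaths. It shows no difference when survivors are unchanged and late deaths are equal, and it merely dilutes the mortality gap when survivors improve and late deaths are equal. The sizes given rest on an assumed scale, Day 29 mean, survivor change and death shares; the ordering of early and late deaths follows from the rule alone. It would be wrong to conclude that the whole HRQoL summary misleads, because its raw scores behave properly. The primary analysis and its power are untouched.

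Question 2 as printed in Appendix K is ambiguous for its stated pre-sepsis comparison. This affects the question 2 output only, not the component or scale scores.

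The point is worth acting on because it concerns a named secondary objective and the change is cheap. The form correction is the more urgent part, since answers already collected cannot be repaired.

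**What to change.** For section 13.3.8:

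- Make the raw Day 29 and Day 90 scores by arm, with death given the worst score, the ITT display. Add quartiles to the planned medians.
- Drop change from Day 29 in that summary.
- Show change only for patients alive at both visits, labelled as descriptive and limited to survivors.
- State that the reference value for PRO change is Day 29, since the general baseline definition in section 13.1 cannot apply.

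For Appendix K, change all five answer options of question 2 to the one-year reference, and do the same in any fielded or translated form that carries the one-week wording. Summarise forms completed before the correction separately from those completed after it.

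The cost is revised table-shell wording and one corrected questionnaire page, with its translations and ethics notification. No additional data collection is needed.
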